Institutional Registry of Hip Fracture in the Elderly

NCT 02279550

March 17th, 2023

Institutional Registry of Hip Fracture in the Elderly

Study protocol

BACKGROUND

Clinical registries comprise a set of selectively collected and stored data focused on a specific condition. The information stored in a registry is generated through a process of prospective data collection focus on data quality to detect errors and thus ensure data integrity. Systematic data collection is characteristic of a well-designed registry and its quality depends directly on the completeness and validity of the data contained [1]. Hip fracture is a frequent complication of osteoporosis in elderly patients [2]. The elderly have weaker bones and are more likely to fall due to comorbidities, instability, polypharmacy, and difficulty maneuvering around environmental hazards. Hip fractures substantially increase the risk of death and major morbidity in this population [3]. In-hospital 30-day mortality in patients admitted for hip fracture is around 6.5%, considering heart and respiratory failure as the main causes of death. Moreover, 13.5% of patients die within 6 months [4]. Of those who survive at 6 months, only 50-60% recover the ability to walk, and 40-50% regain their previous level of independence in basic activities of daily life [5]. Worldwide, the total number of hip fractures is expected to surpass 6 million/year by the year 2050 [5,6], with more than 70% of the new fractures occurring in Asia, Latin America, the Middle East and Africa [7]. Limited data regarding hip fractures is available from Latin America [8]. Several hip fracture registries have been developed worldwide: the National Hip Fracture Database (NHFD) and the Irish Hip Fracture Database in Europe; the Australian and New Zealand Hip Fracture Registry (ANZ HFR) in Oceania; the British Columbia Hip Fracture Registry (IHFD) in North America. Currently, there are no hip fracture registries on-going in Latin America [9]. In 2015, the total population of Argentina is estimated to be close to 43.5 million, with 5 million inhabitants aged \geq 65 years. The population is expected to increase 28% by 2050 and will reach 53 million, with the over 65's population reaching over 10 million¹⁴. Each year approximately 5700 patients are hospitalized due to hip fractures in Argentina. The incidence of hip fractures is increasing in our country due to the advancing age of the population, with an interannual growth rate of 1.4%, resulting in an increasing demand on the health services [10]. The mean annual rate of hip fractures, is 488/100 000 inhabitants aged above 50 years, with a 2.6:1 female to male ratio [11]. In this scenario, due to the large number of patients with hip fracture in our hospital, and the high rate of complications associated, we propose the creation of an institutional registry of elderly patients with hip fracture called "Registro Institucional de Ancianos con Fractura de Cadera" (RIAFC) which was established and initiated at the Hospital Italiano de Buenos Aires (HIBA) in July 2014. We hope this registry will reveal how this disease affects the elderly in our environment, allowing us to evaluate different strategies of care and outcomes.

Primary Objective The main aim of the RIAFC is to collect epidemiological and clinical data on elderly population with hip fractures regarding risk factors, diagnosis, treatment, prognosis, follow-up and mortality, as a basis for improved orthogeriatric co-management, enhancing patients' outcomes, safety and quality of attention.

Secondary Objectives for RIAFC are to describe the population with hip fractures in the HIBA, predisposing factors and triggers for hip fracture, rate of complications associated with hip fracture and their treatment and to describe the clinically relevant outcomes such as in-hospital and long-term morbidity and mortality.

METHODS

The RIAFC takes place at the Hospital Italiano de Buenos Aires, a community-based tertiary care hospital with 650 beds. Information about the patient, the fracture, and the treatment is collected prospectively from personal interviews and from the hospital's electronic clinical records. We include patients over 65 years, with hip fracture, admitted to any medical or surgical unit in the Hospital Italiano de Buenos Aires (HIBA) from July 2014 onwards. We exclude patients who refuse to participate in the RIAFC or to give oral informed consent. We exclude patients with periprosthetic, subtrochanteric and pelvic fracture, hip fracture caused by traumatic injury and pathologic hip fracture.

Hip Fracture Definition We define hip fracture as a femur fracture above the distal part of the lesser trochanter.

Design Prospective registry with consecutive incident cases capture, standardized evaluation, monitoring, and follow up at 12 months. This study is not a clinical trial clinical investigation or a clinical study in which human subject(s) are prospectively assigned, according to a protocol, to one or more interventions (or no intervention) to evaluate the effect(s) of the intervention(s) on biomedical or health-related outcomes, as stated 42 CRF part 11).

A pilot study was performed to assess the validity of the registry's instruments for data collection. This allowed us to calculate the time needed to complete the form, the completeness and comprehensiveness of the included questions, the accuracy of data entry and missing data detection. The registry contains information on patient's baseline demographics, American Society of Anesthesiologists (ASA) and Charlson comorbidity index. To evaluate variables proper of elderly population we included the Barthel index of activities of daily living, Lawton and Brody instrumental activities of daily living scale, Clinical Frailty Scale, physical status classification, Mini-Nutritional Assessment, Parker Mobility Score, EuroQol-5 Dimension Questionnaire, Social Support Inventory.

Chirurgic type of fracture was evaluated according to the Müller AO classification. Relevant clinical information prior to the fracture includes bone mineralization disorders, circumstances around the fall and regular medication. Treatment related variables include fracture treatment, postoperative complications and rehabilitation outcomes. Follow up is performed by telephone interview using structured evaluation to assess physical function, health perception, venous thromboembolism prophylaxis, late postoperative complications, readmissions and mortality.

Data Collection and Management. Quality control strategies All hip fracture incident cases are captured by an automatic real time alert. This alert is generated on the moment the patient is admitted to the hospital with a hip fracture diagnosis, encoded (SNOMED CT) in the hospital's computerized clinical record chart. During the first two months from the beginning of the recruitment we performed a double checked system where every potentially included patient was reported by physician in charge who actively assessed patients with hip fracture in admission wards. The rules that trigger the alert were modified using the information generated by this manual/automatic double-check in order to improve the sensitivity and specificity of the alert. A trained research fellow assesses eligible patients and determines inclusion and exclusion criteria. Patients that meet the inclusion criteria and none of the exclusion criteria are included if they agree to participate through the informed consent process. A standardized and structured interview, including oral questionnaires and forms, is performed and completed. All data collectors have a training period in which they attend academic discussions with the physicians and orthogeriatrics involved. They are trained in data collection, electronic databases and data entry. They receive coaching to

perform the follow-up evaluation by telephone calls, supervised by a research fellow. Data collectors check the completeness of the records of each patient. A data cleaning process is frequently performed to identify and correct all discrepant data. Missing values, inconsistencies, outliers, and other data problems are identified using queries and completed reassessing the patient and the original clinical records.

Laboratory results and ancillary tests are obtained from secondary databases using the higher-quality validated sources available. Administrative and hospitalization data is collected with secondary databases and information from the hospital's computerized clinical health records. All data are automatically backed up daily with redundant storage in a protected off-site location. To protect the patient's confidentiality, the database assigns an external unique administrative subject identifier (subject ID). Follow-up is established every three and twelve months. The follow-up call has two different instances; the clinical and the orthopedist follow-up. As the patients reach 12 months since the inclusion the clinical evaluation includes a telephone follow-up where we ask for any post operatory comorbidities and the orthopedist follow-up consists on patient's visit to the orthopedist clinic. An integrated electronic system ensures at least one of both types of follow up for all patients included. The electronic CRF was encoded in an exhaustive and mutually exclusive way limiting responses to a range of coded values. Data entry is made by a different research fellow who collects clinical data. In this instance, we perform a second check of data quality. Weekly meetings with medical staff specialized in orthogeriatrics are placed to discuss ambiguous or difficult cases.

Indicators: performance indicators are monitored weekly. Weekly reports are performed in order to detect alterations in the number of included and excluded patients, loss of patients' evaluation, number of patients for follow-up. This strategy aids early detection of any problem in the recruitment and inclusion process.

Operations Manual: Acts as a guide to define evaluation strategies and quality control of all the processes involved in collecting and maintaining registry cases. This document standardizes the procedures and processes of the registry to reduce inter-observer variation in data collection, assuring the accuracy of the registry data.

Statistical Analysis Continuous variables are shown as mean and standard deviation or median and interquartile range, according to the observed distribution. Categorical variables are expressed as absolute numbers and percentages. Prevalence rates are expressed with its 95% confidence interval (95% CI). Comparisons between groups are made with Chi-Square test for categorical variables and the Mann-Whitney U test for continuous variables. Survival at one year is estimated with the Kaplan-Meier estimator. Median survival is expressed with its 95% confidence interval (95% CI). Significance will be defined as $p<0.05$. All data analyses will be performed with Stata 14 software.

Ethics: Each patient give oral consent to be included into the registry. The patient's family consent is required if the patient is not able to give or withhold consent. The registry was approved by an Ethics Review Board. This study is not a clinical trial clinical investigation or a clinical study in which human subject(s) are prospectively assigned, according to a protocol, to one or more interventions (or no intervention) to evaluate the effect(s) of the intervention(s) on biomedical or health-related outcomes, as stated 42 CFR part 11).

This study is eligible for written informed consent exemption according to CIOMS rule 10; besides it is not an applicable clinical trial for which registration information is required to be submitted.

[1] Goldberg J, Gelfand HM, Levy PS. Registry evaluation methods: a review and case

study. *Epidemiol Rev* 1980;2:210–20.

[2] Williams TF. Osteoporosis and hip fractures: challenges to investigators and clinicians. *JAMA* 1990;263:708–9.

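### Does excluding fractures caused by traumatic injury undermine the objective of describing what triggers hip fracture?

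*Protocol*

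**What the plan says.** Under Secondary Objectives, the protocol aims to "describe the population with hip fractures in the HIBA, predisposing factors and triggers for hip fracture". It does not limit this to low-energy or fragility fractures.

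The Methods give the exclusions in one sentence: "We exclude patients with periprosthetic, subtrochanteric and pelvic fracture, hip fracture caused by traumatic injury and pathologic hip fracture". No mechanism, energy level or fall height is attached to the phrase "hip fracture caused by traumatic injury". The Hip Fracture Definition is purely anatomical: "We define hip fracture as a femur fracture above the distal part of the lesser trochanter".

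Two other places bear on what is meant. The Background explains why older people fall and includes "difficulty maneuvering around environmental hazards" among the reasons. The description of registry content lists, as pre-fracture information, "bone mineralization disorders, circumstances around the fall and regular medication".

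On procedure, a trained fellow decides eligibility (Data Collection and Management), specialist staff meet weekly to settle unclear cases, and an Operations Manual, not shown, standardises the registry's processes. Under Indicators, weekly reports serve to "detect alterations in the number of included and excluded patients". No breakdown by reason is mentioned.

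**The concern.** A trigger is a cause, and the exclusion works on cause. Under the anatomical definition, a fracture excluded as traumatic is still a hip fracture treated at the hospital. A table of triggers headed as the profile of the hospital's whole hip fracture population would therefore leave out part of that population.

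The undefined term adds to this. Read literally, a fall is a traumatic injury, so the criterion could be taken to remove the very cases the registry exists for. Even on a sensible reading, the line between an ordinary fall and major trauma is not drawn in the protocol, and two assessors might draw it differently.

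What would be at stake is the reported distribution of triggers. Nothing in the document shows that complication or mortality rates would move. They would do so only if the borderline cases had different outcomes.

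**Working it through.** **Setting the texts side by side**

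1. *Is an ordinary fall excluded?* No. The registry records "circumstances around the fall" for its patients, which would be pointless if falls were grounds for exclusion. The Background presents falls as the route to fracture in this age group. The literal reading of traumatic therefore cannot be the intended one.
2. *Are falls over environmental hazards an open case?* The text gives no reason to think so. The Background names such hazards in the sentence that explains why older people fall, which places these falls inside the target population. The document offers no other example of a borderline case.
3. *Does the objective contradict the exclusion?* The same objective also omits the age limit and the exclusions of periprosthetic, subtrochanteric and pathologic fractures. All of these restrict the population, and the reader applies them because the eligibility criteria govern who is described. The traumatic-injury exclusion is no different in kind.
4. *Do triggers still vary among those included?* Yes. Comorbidity, instability, medication and environmental hazards can all differ between enrolled patients. The exclusion removes one class of cause and leaves the rest to be described.

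**Size**

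The protocol gives no figure to reproduce: no number excluded as traumatic and no trigger share. The following is for scale only.

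Let *e* be the share of otherwise eligible fractures excluded as traumatic, *p* the true share of a given trigger among all otherwise eligible fractures, and *x* the part of *p* that falls among the excluded cases (0 ≤ *x* ≤ *e* when *e* ≤ *p*). Then

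reported share = (*p* − *x*) / (1 − *e*).

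Both *e* and *p* are assumed. With *p* = 60%:

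| Assumed *e* | 1/(1 − *e*) | *x* = 0 (no excluded case has the trigger) | *x* = *p·e* (trigger equally common among the excluded) | *x* = *e* (every excluded case has the trigger) |
|---|---|---|---|---|
| 1% | 1.01 | 0.60/0.99 = 60.6% | 0.594/0.99 = 60.0% | 0.59/0.99 = 59.6% |
| 5% | 1.05 | 0.60/0.95 = 63.2% | 0.57/0.95 = 60.0% | 0.55/0.95 = 57.9% |
| 10% | 1.11 | 0.60/0.90 = 66.7% | 0.54/0.90 = 60.0% | 0.50/0.90 = 55.6% |

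A trigger that is wholly excluded is reported at 0%, and one wholly retained is inflated by 1/(1 − *e*). Those two results hold only when each trigger lies entirely on one side of the line. A blurred boundary, or a trigger such as medication that can coexist with an excluded injury, gives the general formula, and the shift may then go either way or vanish.

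In every column the reported share is the correct share among eligible patients. It differs from *p* only if the table is read as covering excluded patients too.

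**The case for a change.** The best case for a change is this. Objectives and eligibility criteria belong in the protocol, so the definition cannot be left to a statistical analysis plan. The fellow, the weekly meetings and the manual may make decisions consistent, but they cannot return excluded causes to the data or tell a reader of the protocol where the line lies. The weekly counts, as described, are not split by reason, so the excluded share might not be reportable. Enrolment has no stated end date, so a clarification could still help, and it would cost a definition, a few words and one extra count.

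Part of this stands. The term is undefined in the protocol, the objective is worded more broadly than the population enrolled, and the pathologic-fracture exclusion raises the same point about scope.

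The rest does not make a defect. Operational definitions of this kind commonly sit in an operations manual, and the absence of one from a short protocol does not show that the study lacks it. Nor does the protocol say that exclusion reasons go unrecorded: the fellow must identify the criterion in order to apply it. The harm also depends on a later mislabelling of the trigger table, and the Statistical Analysis section prescribes no hospital-wide trigger distribution. A low cost does not turn a wording preference into a needed change when no result is shown to alter.

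**Conclusion.** No change is needed. The protocol is loose about scope on this point but does not contradict itself. Followed as written, the registry gives a sound description of triggers among its eligible patients, and an analyst would report the table for that group as a matter of course, next to the eligibility criteria.

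The size of any difference from the hospital's whole hip fracture population cannot be derived from the document. On the assumed figures it is at most 0.6 percentage points on a 60% share when 1% of fractures are excluded. It lies between −4.4 and +6.7 points when 10% are excluded, depending on how the trigger is distributed among the excluded cases.

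The conclusion rests on two readings: that ordinary falls are eligible, which the Background and the recorded data items support, and that the fellow, the weekly case meetings and the Operations Manual keep the boundary reasonably consistent. The second is plausible from the procedures described but cannot be verified, because the manual is not shown.

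### Do an unstated reference period for the baseline scales and an open-ended rule for filling gaps undermine the registry's baseline data?

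*Protocol*

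**What the plan says.** The Methods paragraphs on registry content open with "The registry contains information on patient's baseline demographics" and two comorbidity and physical-status measures. They then name the scales chosen for an elderly population: "Barthel index of activities of daily living, Lawton and Brody instrumental activities of daily living scale, Clinical Frailty Scale", followed by nutrition, mobility, quality-of-life and social-support instruments. No period of reference is attached to any of them.

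One later sentence does set a pre-fracture period: "Relevant clinical information prior to the fracture includes bone mineralization disorders, circumstances around the fall and regular medication". It names none of the scales. The same paragraph has physical function and health perception assessed again by telephone, and the follow-up times given are three and twelve months.

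Under Data Collection and Management, cases are captured by an alert at admission, and then "A standardized and structured interview, including oral questionnaires and forms, is performed and completed". No day relative to fracture, admission or surgery is given. Cleaning is described as frequent, and its rule is: "Missing values, inconsistencies, outliers, and other data problems are identified using queries and completed reassessing the patient and the original clinical records". There is no latest date, and no distinction between fixed items and items that change over time.

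**The concern.** Every interview takes place after the fracture, so each scale could in principle be scored for either period. For mobility and daily activities the two scores are different variables. Set against a pre-fracture score, a three- or twelve-month value measures return to the earlier state. Set against an in-hospital score, it measures improvement since the injury. The Background describes recovery in the first sense, reporting that "40-50% regain their previous level of independence in basic activities of daily life". A secondary objective is to describe factors that predispose to hip fracture, and function or frailty can serve as such a factor only if it describes the patient beforehand.

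The completion rule could add to this in two ways. If a missing score is filled weeks or months later by scoring the patient as found, post-fracture status enters the record as baseline. And a gap that only the patient can fill can be closed only while the patient is alive and reachable, so completeness of these items could depend on survival. Descriptions and group comparisons using the scales would be exposed to both.

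**Working it through.** This is mainly a check of text; the protocol gives no figure to reproduce.

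**1. Are the silences real?** Yes. None of the named scales has a stated reference period, and no time limit is stated for completing values by reassessing the patient. The word baseline is attached to demographics and does not define a period for the scales. The verb in the pre-fracture sentence introduces examples, so it neither includes nor excludes them.

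**2. Does the protocol state anything wrong or contradictory?** No. The list of scales is an inventory. The completion rule describes ordinary source verification: find the problem, go back to the patient and the records, correct it. It does not say that a late current-status score replaces a baseline value.

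**3. When would late completion do harm?**
- If the item asks about the time before the fracture, a late query asks the same question. What is lost is accuracy of recall, and the original records offer a second source.
- If the item asks about status at interview, a late query scored as of the later date would be wrong. This needs both that reading of the scale and a long delay.

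**4. What stands between the silence and that harm?** The protocol describes:
- a pilot of the data-collection instruments (registry content paragraphs);
- a standardised interview, a training period for collectors, checks of record completeness and frequent cleaning (Data Collection and Management);
- a second quality check at data entry, made by a different research fellow, and weekly meetings on ambiguous cases (same section);
- an Operations Manual whose stated purpose is to standardise procedures and limit differences between observers.

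Different interviewers reading a scale differently is exactly the problem the last item is meant to prevent. Whether it fixes these two points cannot be seen.

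**5. Which planned analyses depend on it?** The Statistical Analysis section lists descriptive summaries, prevalence with confidence intervals, two-group tests and Kaplan-Meier survival at one year. It specifies no change from baseline and no mortality analysis restricted to records with complete scales. Overall survival does not use the scales. Descriptions and comparisons that use them do carry the ambiguity.

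**6. Can a size be given?** Not from the protocol, which reports no gap rate, query delay or score distribution. An unfavourable illustration of the survivor effect runs as follows.
- Inputs from the Background: 6.5% dead at 30 days (quoted there as in-hospital mortality) and 13.5% within 6 months, read as cumulative.
- Assumptions: the hazard from month 1 to 6 continues to month 12; 10% of records have a gap only the patient can fill; every query is raised at 6 months; everyone then alive is completed; nothing is recovered from records.
- Monthly hazard: ln(0.935/0.865)/5 = 0.01556.
- Twelve-month survival: 0.865 × exp(−6 × 0.01556) = 0.788, so mortality is 21.2%.
- Share of those deaths before the query: 0.135/0.212 = 0.636.
- Mortality among complete records: 0.212 × (1 − 0.10 × 0.636) / [0.212 × (1 − 0.10 × 0.636) + 0.788] = 20.1%.
- Difference: 21.2 − 20.1 = 1.1 percentage points. With a 5% gap and queries at day 30, the complete-record figure is 20.95%, about 0.3 points low.

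The gap rates and delays are invented. No recovery from records contradicts the completion rule, and six-month queries sit badly with frequent cleaning. The result shows scale only, for a quantity the plan does not report.

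**The case for a change.** The best case for acting is that a reference period defines the variable. It is not an analysis detail, and no analysis plan can restore it if interviewers never recorded it. The objective on predisposing factors needs pre-fracture values, and follow-up function invites a comparison with baseline even though none is specified. The Operations Manual is described only in general terms, and the weekly reports are said to track inclusions, exclusions, lost evaluations and follow-up counts, not the age of queries. The remedy would be cheap: a sentence or two, and a date and source for each completed value.

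Much of this stands as description. The protocol is silent, and a reader cannot tell from it alone which status a given score represents. What does not follow is that the registry is doing something wrong. A short registry protocol that lists its instruments and refers procedure to a manual leaves detail to the expected place. New wording could not by itself settle what was recorded since July 2014; only the forms and the manual can do that. A strict cut-off, after which only records count, is also a debatable exchange: it would discard patient or family recall of pre-fracture status, which may be the only source for some items, and would raise the reported missing rate. Reporting completeness by vital status is a matter usually left to the analysis plan.

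**Conclusion.** The observation is correct, but it is a gap that the registry's own procedures can be expected to fill, and no change to the plan is called for. No stated rule produces a wrong result, no planned analysis is shown to be wrong, and the overall one-year survival estimate is unaffected. The size of any effect on the scales is unknown. The survivor effect, under assumptions chosen to be unfavourable, is about 1 percentage point in an estimate the plan does not make.

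This rests on two assumptions: that the structured form and the Operations Manual apply one reference period per scale, and that queries about a scale ask about that same period. If an analyst later reports change from baseline or treats these scores as predisposing factors, the reference period on the form should be confirmed first. That is ordinary care in using registry data and needs no revision of the protocol.

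### Group comparisons of follow-up function are fixed as unadjusted tests in a non-randomised registry that already holds baseline function scores

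*Protocol*

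**What the plan says.** On what is collected, the Methods say that "we included the Barthel index of activities of daily living, Lawton and Brody instrumental activities of daily living scale", and the same list continues with "Parker Mobility Score, EuroQol-5 Dimension Questionnaire, Social Support Inventory". On later assessment they say "Follow up is performed by telephone interview using structured evaluation to assess physical function, health perception", followed by complications, readmissions and mortality. The follow-up instruments are not named. Data Collection and Management sets follow-up at three and twelve months. The registry also records rehabilitation results: "Treatment related variables include fracture treatment, postoperative complications and rehabilitation outcomes".

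On analysis, the Statistical Analysis section gives display rules by type of variable. For continuous data the rule is "Continuous variables are shown as mean and standard deviation or median and interquartile range, according to the observed distribution", and categorical data are shown as counts and percentages. Groups are compared by chi-square (categorical) or Mann-Whitney U (continuous), and one-year survival is by Kaplan-Meier. No regression, covariate adjustment or paired method is named.

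On purpose, the Background hopes the registry will let the hospital assess alternative ways of delivering care. The Design paragraph describes a prospective registry of consecutive cases and says it assigns no interventions.

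**The concern.** Groups in a registry form themselves: by type of treatment, admitting unit, residence, frailty or calendar period. Such groups will often differ in function before the fracture. An unadjusted test of twelve-month function then mixes two things: what happened after the fracture, and who was more independent beforehand. A service that admits frailer patients would look worse even if its patients lost no more function than others.

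The information needed to separate the two is already in the registry, yet the only comparative methods the protocol names do not use it. What is at stake is the interpretability of comparisons of follow-up function, and some of their precision. Mortality estimation by Kaplan-Meier is not affected.

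**Working it through.** The protocol states no sample size, power or expected difference, so there is no figure of its own to reproduce. The check has three parts.

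**1. Variance removed by adjusting for baseline**

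Input: correlation ρ between baseline and follow-up score. The protocol gives none; 0.5 to 0.7 is assumed. Under a linear model the residual variance after adjustment is (1 − ρ²) times the unadjusted variance, and the equivalent sample multiple is 1/(1 − ρ²).

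| ρ | 1 − ρ² | Variance removed | Equivalent sample multiple |
|---|---|---|---|
| 0.5 | 0.75 | 25% | 1.33 |
| 0.6 | 0.64 | 36% | 1.56 |
| 0.7 | 0.51 | 49% | 1.96 |

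The last column is an upper limit here. When groups differ at baseline, group and baseline score are correlated, and part of the gain is lost in separating them.

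**2. Baseline difference carried into the unadjusted comparison**

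Suppose two groups differ at baseline by D standard deviations, follow-up is linear in baseline with the same slope in both, and group has no effect of its own. The expected follow-up difference is then ρ × D standard deviations. At ρ = 0.5 to 0.7, between 50% and 70% of the standardised baseline difference appears at follow-up as an apparent group difference. Adjustment for baseline removes this term. D is unknown, so no absolute size can be given. Each score is in its own standard deviation units, so the two scales need not be the same.

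**3. Why within-patient recovery is worth reporting as well**

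Let b be the share independent at baseline and f the share independent at follow-up. From b and f alone, the share of initially independent patients who are independent at follow-up lies between max(0, b + f − 1)/b and min(b, f)/b. With assumed values:

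- b = 0.60, f = 0.40: from 0/0.60 = 0% to 0.40/0.60 = 66.7%.
- b = 0.80, f = 0.50: from 0.30/0.80 = 37.5% to 0.50/0.80 = 62.5%.

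Separate levels at two times therefore leave recovery wide open; it must be derived patient by patient. The denominator matters too. The Background cites "13.5% of patients die within 6 months" and, among six-month survivors, "40-50% regain their previous level of independence in basic activities of daily life". Per admitted patient, the latter range becomes 0.40 × (1 − 0.135) = 34.6% to 0.50 × (1 − 0.135) = 43.3%.

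**The case against.** The strongest objection is that derived variables, paired methods and covariate adjustment are commonly left to a statistical analysis plan, which is not shown. That holds for the definition of recovery: its absence alone would be missing detail. It has less force for group comparisons, because the protocol does make a choice there and names two unadjusted tests.

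Three stronger readings are tempting, and the document supports none of them.

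- A reader might infer that the plan cannot yield recovery. The display rules are generic. A change score is a continuous variable and a return to previous level is a categorical one; both fit the rules, and neither is excluded.
- A reader might take the Background's recovery percentages as the benchmark the registry must match. They are cited context on six-month survivors, never called a target. Follow-up is at three and twelve months, and no objective names functional recovery.
- A reader might infer that baseline and follow-up will be compared as if they were independent samples. The named tests are for comparisons between groups, and nothing proposes using them on the same patients at two times. No penalty for ignored pairing should be attached to the plan.

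Two further points stand. In non-randomised groups, adjustment changes the question as well as the precision: it asks about follow-up function among patients with the same starting point. And the correlations are assumptions; at ρ of 0.5 to 0.7 baseline explains only 25% to 49% of follow-up variance, so it would be wrong to say that an unadjusted comparison mostly reflects prior function.

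**Conclusion.** The point holds as a low-cost improvement to a stated analysis choice. It is not a contradiction, and no figure in the protocol changes. Followed as written, any group comparison of follow-up function or health perception would carry pre-fracture differences into the result and forgo a reduction in residual variance of 25% to 49%.

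This rests on an assumed correlation of 0.5 to 0.7, an approximately linear relation, and the listed scales describing the patient at inclusion and, ideally, before the fracture. The Methods attach the word baseline to demographics and do not date each scale, so the last assumption should be confirmed. Adjusting for one score does not remove confounding by age, comorbidity or frailty, nor the selection that arises because only survivors have a follow-up score.

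**What to change.** In Statistical Analysis, add wording such as: *Group comparisons of follow-up physical function and health perception are adjusted for the patient's own baseline score, by linear or ordinal regression as the scale requires. The Mann-Whitney U test is descriptive for these outcomes.* This does not require the same instrument at both times; a related baseline scale will serve.

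Where the same scale was recorded at both times, also report within-patient change and the proportion back at or above the patient's own baseline, with a 95% confidence interval. State whether the denominator is survivors or all included patients and how deaths are counted. Show the proportion by baseline level, because a survivor already in the lowest category counts as recovered automatically. In Methods, name the follow-up instruments and say what time the inclusion scores refer to.

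Cost: wording and modest analysis work, with no new data for the adjusted comparison. Patients without a baseline score drop out or need imputation, and the number affected should be reported. If a scale was not repeated at follow-up, change and recovery cannot be computed on it for patients already followed; adjustment still can.
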